7.2. Recording Adverse Events and Serious Adverse Events

Recording of adverse events and serious adverse events:

 1. The investigator or site staff will be responsible for detecting, documenting and reporting events that meet the definition of an AE or SAE. 2. The investigator or site staff will then record all relevant information regarding an AE/SAE in the CRF. 3. There may be instances when copies of medical records for certain cases are requested by GSK. In this instance, all subject identifiers, with the exception of the subject number, will be blinded on the copies of the medical records prior to submission to GSK. 4. The investigator will attempt to establish a diagnosis of the event based on signs, symptoms, and/or other clinical information. In such cases, the diagnosis will be documented as the AE/SAE and not the individual signs/symptoms. Clinical AEs will be described by diagnosis and not by symptoms when possible (e.g., upper respiratory tract infection, seasonal allergy, etc. instead of runny nose). 5. AEs will be collected from the start of the provisional MEDu irradiation procedure and until 5 days following last administration of the study product. 6. SAEs will be collected over the same time period as stated above for AEs. However, any SAEs assessed as related to study participation (e.g., investigational product, protocol mandated procedures, invasive tests, or change in existing therapy) or related to a GSK concomitant medication will be recorded from the time a subject consents to participate in the study up to and including any follow-up contact. 7. Medical conditions reported prior to the time period for reporting AEs/SAEs should be recorded as part of the subject's medical history.

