Amendment No.:	Non-Substantial/Minor 		Informed Consent  Yes  No Safety Statement  Yes  No CRF  Yes  No		Signature:
Protocol Version No.:	Substantial/ Major 				Date:

 GlaxoSmithKline	Document Name	207640 Protocol.doc		
	Type	Version	Document Identifier	Effective Date
	eldo_controlled	2.0; Most-Recent; Effective; CURRENT	090032d580d3df08	11-May-2017 13:45:31
	Reason For Issue	Auto Issue		

SCHEDULE OF EVENTS

Procedure/Assessment	Visit 1	Visit 2 ¹ 0-7 Days after Visit 1	Visit 3 1 Day after Visit 2	Visit 4 ¹ 0-7 Days after Visit 3	Visit 5 1 Day after Visit 4
	Subject Screening	Provisional MED Irradiation (UV exposure)	Provisional MED Determination	Test Irradiation (UV exposure)	MEDp and MEDu Determination and SPF Calculation for Test and Reference Sunscreen
Informed Consent	X				
Demographics	X				
Medical History	X				
Current / Concomitant Medication	X	X ²	X	X ²	X
Individual Typology Angle (ITA°)	X				
Fitzpatrick Skin Type Assessment	X				
In/Exclusion Criteria	X	X ^{2,3}			
Subject Eligibility	X	X ²			
Continued Eligibility		X ²	X	X ²	X
Randomisation		X			
Provisional Minimum Erythral Dose (MEDu) Irradiation		X			
Visual Grading of Exposure Sub-Sites (Test Sites) ⁴			X		X
Study Product Application to Randomly Assigned Test Sites on the Back				X	
Study Irradiation				X	
Adverse Events		X	X	X ²	X
Subject Discharge from Study					X

1. Visit 2 may be combined with Visit 1; Visit 4 may be combined with Visit 3. If these visits are not combined, they must happen within 7 calendar days of one another. Therefore, the total duration of the study for each subject could range from 3 to 16 calendar days.
2. Not required if this visit is combined with the previous visit.
3. To include a review of exclusion criteria in Appendix 2.
4. Visual Grading of skin must happen 16-24 hours after irradiation.

 GlaxoSmithKline	Document Name	207640 Protocol.doc		
	Type	Version	Document Identifier	Effective Date
	eldo_controlled	2.0; Most-Recent; Effective; CURRENT	090032d580d3df08	11-May-2017 13:45:31
	Reason For Issue	Auto Issue		

PROTOCOL SYNOPSIS FOR STUDY 207640

Brief Summary

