7.4. Reporting Adverse Events and Serious Adverse Events

AE Reporting to GSKCH:

 1. AEs will be recorded in the AE section of the CRF. 2. Medical conditions recorded by the subject on a diary card or similar document that meet the definition of an AE must also be recorded in the AE section of the CRF, if not previously well-characterized by the investigator in the subject’s medical history. 3. AEs elicited by the investigator in a standard manner at the study visits should also be recorded in the AE section of the CRF. The investigator or designee

 GlaxoSmithKline	Document Name	207640 Protocol.doc		
	Type	Version	Document Identifier	Effective Date
	eldo_controlled	2.0; Most-Recent; Effective; CURRENT	090032d580d3df08	11-May-2017 13:45:31
	Reason For Issue	Auto Issue		

must ask the subject the following question during each visit including any follow-up visits: ***“Have you felt unwell, experienced any symptoms or taken any medication (since your last visit) (today) (since your last dose) (since the last session)?”***

4. The medically qualified investigator should review adverse events in a timely manner; this review should be documented in writing in the source document or in the CRF.
5. After the study is completed at a given site, and the site has received their study data on Compact Discs (CDs), the electronic data collection tool will be removed from the internet to prevent the entry of new data or changes to existing data.

SAE Reporting to GSKCH:

A paper copy of the SAE form provided in the investigator study master file should be completed as fully as possible.

It is essential to enter the following information:

1. Protocol and subject identifiers
2. Subject’s demography
3. Description of events, with diagnosis if available
4. Investigator opinion of relationship to study product (see section 8.3)
5. Criterion for seriousness.

The following are desirable and are of particular relevance for investigator and GSKCH assessment of the SAE report:

1. Date of onset of AE
2. Date AE stopped, if relevant
3. Study product start date
4. Study product end date if relevant
5. Action taken on study product
6. Outcome if known

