1.4 Timepoints and visit windows

Deviations from the scheduled assessment times must be avoided. The following are the assessment time windows.

Visit	Time window
Visit 2	0-7 days after Visit 1 (allowed to be combined with Visit 1)
Visit 3	1 day after Visit 2
Visit 4	0-7 days after Visit 3 (allowed to be combined with Visit 3)
Visit 5	1 day after Visit 4

Visual grading of skin at Visit 3 must happen 16-24 hours after irradiation at Visit 2. Visual grading of skin at Visit 5 must happen 16-24 hours after irradiation at Visit 4.

2 Data analysis

Data analysis will be performed by inVentiv Health Clinical. Prior to database hard lock a Blind Data Review Meeting (BDRM) will be conducted in which various aspects of the trial will be discussed and agreed. The statistical analysis software used will be SAS® version 9.4.

All listings will be produced for all randomised subjects, unless otherwise specified.

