eldo_clinical_doc	1.0; CURRENT; Most-Recent; Effective	090032d580dcf91b	(8-Dec-2017 11:01:02			
Reason For Issue	Imported as Effective from Legacy System					

Confidential

Forte/207640

Page 29

Protocol: 207640

Page x of y Program Run Date:ddmonyyyy

Listing 16.2.6 Individual Subjects Efficacy Data Randomised Population

Subject	Age/Sex/Race[1]	Visit	Test-	Sub-Site	Treatment	Variable	Variable Value	Valid /	Exclusion Justification
Number			Site					Excluded	
PPD						Provisional	x.xx		
						MEDu			
						MEDu	x.xx		
						MEDp test	x.xx		
						MEDp reference	x.xx		
						SPFi test	XX.X	Valid	
						SPFi reference	XX.X	excluded	invald fortest product
						Provisional	x.xx		
						MEDu			
						MEDu	x.xx		
						MEDp test	x.xx		
						MEDp reference	x.xx		
• • •						SPFi test	XX.X		
						SPFi reference	XX.X		

[1] Age in years; Sex: F = Female, M = Male; Race: A = Asian, B = Black or African American, I = American Indian or Alaska Native, H = Native Hawaiian or Other Pacific Islander, W = White, O = Multiple.

Program: PPD Source: PPD

Note to programmer: Check actual races captured in eCRF to adjust the race name and abbreviations.

Document Name	16.1.7 Documentation of statistical methods.pdf				
Туре	Version	Document Identifier	Effective Date		
eldo clinical doc	1.0; CURRENT; Most-Recent; Effective	090032d580dcf91b	8-Dec-2017 11:01:02		
Reason For Issue	Imported as Effective from Legacy System				

GSK Consumer Healthcare

Confidential

Forte/207640

Statistical Analysis Plan

Page 30

Protocol: 207640

Page x of v Program Run Date:ddmonyvyv

Source: PPD

Listing 16.2.7.1 All Adverse Events Randomised Population

Treatment Group: Physiogel Daily Defence/no treatment

Subject Number	Age/Sex/R ace[1]	Adverse Event (Preferred Term) (System Organ Class)	Start Date /Study Day[2]	Start Time	End Date	End Time	Frequency /Intensity [3]	Related to Study Product?	Action Taken re Study Product	Outcom e	Serious ?	Withdrew?[4]
PPD				PPD			Singl e/ MILD	No	NOT APPLICAB LE	RECOVE RED/RE SOLVED	NO	NO

[1] Age in years; Sex: F = Female, M = Male; Race: A = Asian, B = Black or African American, I = American Indian or Alaska Native, H = Native Hawaiian or Other Pacific Islander, W = White, O = Multiple.

- [2] Study day is the day relative to start of treatment, day 1 being the day of first treatment.
- [3] INT = Intermittent and SGLE = Single.
- [4] Did subject withdraw from study as a result of this adverse event?

Program: PPD

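### AE collection is stated to run to 5 days after the last product application, but the last scheduled AE assessment is 1 day after it, so 4 of the 5 days have no scheduled contact

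*Protocol*

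**What the plan says.** **Collection period.** Protocol 7.2, item 5: "AEs will be collected from the start of the provisional MEDu irradiation procedure and until 5 days following last administration of the study product". SAP 2.6.1.1 gives the same period, and 7.2, item 6, applies it to SAEs. For SAEs related to study participation or to a sponsor concomitant medication, item 6 widens it from consent "up to and including any follow-up contact".

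**Duty to detect.** Protocol 7.2, item 1: "The investigator or site staff will be responsible for detecting, documenting and reporting events that meet the definition of an AE or SAE". Under 7.4 the investigator or designee "must ask the subject the following question during each visit including any follow-up visits", and a scripted question follows.

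**Schedule.** The Schedule of Events marks product application at Visit 4 only. The last column with an AE assessment is Visit 5, which also carries "Subject Discharge from Study". SAP 1.4 places Visit 5 "1 day after Visit 4". Footnote 1 of the Schedule says that "the total duration of the study for each subject could range from 3 to 16 calendar days". No later visit, call or diary appears in the Schedule or in the visit lists.

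**After discharge.** Protocol 4.4 follows AEs that are still open at the final visit. Protocol 7.5 does not oblige investigators to look for events in former subjects, but related SAEs that they learn of must still be reported. Protocol 4.6 ends the study at the last subject's last visit.

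**Endpoint.** Protocol section 2 lists AE frequency and severity under the primary objectives, and SAP 1.2 lists it as secondary.

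**The concern.** The plan states a 5-day collection period after application, but its schedule of contacts stops after the first of those days. The references to follow-up contacts and visits in 7.2 and 7.4 do not close the gap, because neither is scheduled. Once a subject is discharged at Visit 5, the former-subject wording in 7.5 can be read as lifting the duty to ask while the stated period is still running.

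The effect falls on the safety endpoint. SAP 2.6.1.1 defines treatment-emergent AEs as those reported after product application. It tabulates them as numbers and percentages of subjects (Tables 14.3.1.1 to 14.3.1.4) in the same section that states the 5-day period. A reader would reasonably take the percentages to reflect 5 days of asking.

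The solicited coverage may be thinner still. In the Schedule of Events, the AE assessment at Visit 4 is marked as not required when Visit 4 is combined with Visit 3, although the visit list in Protocol 3.1 does not exempt it. On the Schedule's reading, Visit 5 can be the only required AE query after application.

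**Working it through.** **Inputs**

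| Quantity | Value | Source |
|---|---|---|
| Visit 1 to Visit 2 | 0 to 7 days | Schedule of Events; SAP 1.4 |
| Visit 2 to Visit 3 | 1 day | same |
| Visit 3 to Visit 4 (only application) | 0 to 7 days | same |
| Visit 4 to Visit 5 (last AE assessment, discharge) | 1 day | same |
| End of AE collection | 5 days after last application | Protocol 7.2, item 5; SAP 2.6.1.1 |
| Application to start of irradiation | 15 to 30 minutes | Protocol 6.4.4 |
| Irradiation to grading at Visit 5 | 16 to 24 hours | Schedule of Events; SAP 1.4 |

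**1. Reproduce the plan's own figure (3 to 16 days per subject).**
- Minimum: 0 + 1 + 0 + 1 = 2 elapsed days, or 3 calendar days counted inclusively.
- Maximum: 7 + 1 + 7 + 1 = 16 elapsed days, or 17 counted inclusively.

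The stated range ends at Visit 5, which confirms that no later contact is planned. The 3 matches the inclusive count and the 16 the elapsed count. This is a side point, but it matters if the footnote is revised.

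**2. Days without scheduled contact, on the SAP's study-day scale.** Footnote 2 of Listing 16.2.7.1 reads: "Study day is the day relative to start of treatment, day 1 being the day of first treatment". Hence:
- Visit 4 = day 1 and Visit 5 = day 2.
- The window closes on day 1 + 5 = day 6.
- Post-application days are days 2 to 6, five in all. Only day 2 has a scheduled contact.
- Days without contact: 5 − 1 = 4 (days 3 to 6), and 4/5 = 80%.

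**3. Does the gap depend on the schedule followed?**

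| Schedule and count | Visit 5 | Window closes | Gap |
|---|---|---|---|
| Shortest, elapsed (Visit 1 = 0) | 2 | 6 | 4 |
| Longest, elapsed (Visit 1 = 0) | 16 | 20 | 4 |
| Shortest, inclusive (Visit 1 = 1) | 3 | 7 | 4 |
| Longest, inclusive (Visit 1 = 1) | 17 | 21 | 4 |

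The gap is always 4 days, because both ends are counted from Visit 4.

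**4. Check in hours.** The documents do not give the irradiation time, so a range of 0 to 4 hours is assumed.
- Earliest grading: 0.25 + 0 + 16 = 16.25 h after application, leaving (120 − 16.25)/24 = 4.3 days.
- Latest grading: 0.5 + 4 + 24 = 28.5 h after application, leaving (120 − 28.5)/24 = 3.8 days.

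So 3.8 to 4.3 of the 5 days follow the last scheduled contact, in agreement with the day count.

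**The case against.** The strongest reply is that nothing contradicts itself. Both documents say that AEs are collected for 5 days. Neither says that they are solicited for 5 days. A recording window that outlasts the last visit, with its tail filled by spontaneous reports, fits both texts. The consent pages were removed, so subjects may have been told to report later events, and the follow-up wording shows that later contact is contemplated.

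Much is also covered elsewhere. AEs open at Visit 5 are followed up, related SAEs remain reportable after discharge, and localised UV erythema is not an AE at all. Exposure is one supervised application per product to a 40 cm² site in at most 25 subjects. Protocol 9.3.3 plans only a listing of AEs, the SAP plans no inference on them, and Listing 16.2.7.1 shows when each recorded event began. Finally, 80% is a share of days, not of events, and no bias can be computed.

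Most of this stands, and it limits the point. Spontaneous reporting is compatible with the wording, no claim is made about what subjects are told, and 80% is not a measure of bias. What remains is new non-serious events that start after Visit 5 and are not volunteered. The start dates in the listing show when recorded events began, not what went unreported. The plan never says that the last 4 days rest on spontaneous report, yet it tabulates percentages under a stated 5-day period. That needs correcting on either reading.

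**Conclusion.** The concern holds. The stated collection period runs 4 days beyond the last scheduled AE assessment in every permitted schedule, which is 80% of its post-application part. No other provision in either document schedules a contact in that time. An unscheduled contact by a site could fill the gap, but nothing requires one.

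The day count rests on the documents' figures alone, and only the hour-based check uses an assumed irradiation time. The consequence is a possible understatement of treatment-emergent AE frequency, confined to new events after Visit 5 that are neither serious nor spontaneously reported. Its size cannot be given, since the documents state no rate or timing for such events. The SPF estimate, its confidence interval, the validity criteria and the stepwise sample size do not depend on it. The correction should be made, but the trial's main result is not at risk.

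**What to change.** Reconcile Protocol 7.2, the Schedule of Events and SAP 2.6.1.1. The sponsor's safety function chooses between two routes.

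**(a) Schedule the contact.** Add one telephone AE contact per subject at the end of the stated window, using the scripted question in 7.4, and give it a column in the Schedule of Events. Correct the duration in footnote 1 and say which count is used: from the working above, 6 to 20 elapsed days or 7 to 21 inclusive days. State that the call does not change the end-of-study definition in 4.6 or the Last Subject Last Visit limit on the restrictions in 3.2. State also whether a subject who misses the call still counts as completed. Cost: at most 25 short calls and one schedule column.

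**(b) State what is solicited.** Say in 7.2, in SAP 2.6.1.1 and in the footnotes of Tables 14.3.1.1 to 14.3.1.4 that solicited AE collection ends at Visit 5. Say that later events, up to 5 days after application, are recorded only if spontaneously reported, and keep the duty to record them. Cost: wording and table footnotes only. The drawback is a less favourable stated window.

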7.3. Evaluating Adverse Events and Serious Adverse Events

Assessment of Intensity:

The investigator or designee will make an assessment of intensity for each AE and SAE reported during the study and will assign it to one of the following categories:
 
 1. Mild: An event that is easily tolerated by the subject, causing minimal discomfort and not interfering with everyday activities.

 GlaxoSmithKline	Document Name	207640 Protocol.doc		
	Type	Version	Document Identifier	Effective Date
	eldo_controlled	2.0; Most-Recent; Effective; CURRENT	090032d580d3df08	11-May-2017 13:45:31
	Reason For Issue	Auto Issue		

2. Moderate: An event that is sufficiently discomforting to interfere with normal everyday activities
 3. Severe: An event that prevents normal everyday activities. An AE that is assessed as severe will not be confused with an SAE. Severity is a category utilized for rating the intensity of an event; and both AEs and SAEs can be assessed as severe.
- Note: An event is defined as ‘serious’ when it meets at least one of the pre-defined outcomes as described in the definition of an SAE.

Assessment of Causality:

 1. The investigator is obligated to assess the relationship between study product and the occurrence of each AE/SAE. 2. A "reasonable possibility" is meant to convey that there are facts/evidence or arguments to suggest a causal relationship, rather than a relationship cannot be ruled out. 3. The investigator will use clinical judgment to determine the relationship. 4. Alternative causes, such as natural history of the underlying diseases, concomitant therapy, other risk factors, and the temporal relationship of the event to the study product will be considered and investigated. 5. The investigator will also consult the Safety Statement, in the determination of his/her assessment. 6. For each AE/SAE the investigator must document in the medical notes (source document) or CRF that he/she has reviewed the AE/SAE and has provided an assessment of causality. 7. There may be situations when an SAE has occurred and the investigator has minimal information to include in the initial report to GSK. However, it is very important that the investigator always make an assessment of causality for every event prior to the initial transmission of the SAE data to GSK. 8. The investigator may change his/her opinion of causality in light of follow-up information, amending the SAE data collection tool accordingly. 9. The causality assessment is one of the criteria used when determining regulatory reporting requirements.

7.4. Reporting Adverse Events and Serious Adverse Events

AE Reporting to GSKCH:

 1. AEs will be recorded in the AE section of the CRF. 2. Medical conditions recorded by the subject on a diary card or similar document that meet the definition of an AE must also be recorded in the AE section of the CRF, if not previously well-characterized by the investigator in the subject’s medical history. 3. AEs elicited by the investigator in a standard manner at the study visits should also be recorded in the AE section of the CRF. The investigator or designee

 GlaxoSmithKline	Document Name	207640 Protocol.doc		
	Type	Version	Document Identifier	Effective Date
	eldo_controlled	2.0; Most-Recent; Effective; CURRENT	090032d580d3df08	11-May-2017 13:45:31
	Reason For Issue	Auto Issue		

must ask the subject the following question during each visit including any follow-up visits: ***“Have you felt unwell, experienced any symptoms or taken any medication (since your last visit) (today) (since your last dose) (since the last session)?”***

4. The medically qualified investigator should review adverse events in a timely manner; this review should be documented in writing in the source document or in the CRF.
5. After the study is completed at a given site, and the site has received their study data on Compact Discs (CDs), the electronic data collection tool will be removed from the internet to prevent the entry of new data or changes to existing data.

SAE Reporting to GSKCH:

A paper copy of the SAE form provided in the investigator study master file should be completed as fully as possible.

It is essential to enter the following information:

1. Protocol and subject identifiers
2. Subject’s demography
3. Description of events, with diagnosis if available
4. Investigator opinion of relationship to study product (see section 8.3)
5. Criterion for seriousness.

The following are desirable and are of particular relevance for investigator and GSKCH assessment of the SAE report:

1. Date of onset of AE
2. Date AE stopped, if relevant
3. Study product start date
4. Study product end date if relevant
5. Action taken on study product
6. Outcome if known

The SAE form, completed as fully as possible, and SAE fax cover sheet must be faxed or e-mailed to the appropriate GSKCH Study Manager as soon as possible, **but not later than 24 hours** after study site personnel learn of the event. The GSKCH Study Manager should be notified of the situation by telephone or email.

Fax Serious Adverse Events to:

UK: PPD [REDACTED]

The GSKCH Study Manager will be responsible for forwarding the SAE form to the Case Management Group, Global Clinical Safety and Pharmacovigilance, the Medical Director responsible for the study and other GSKCH personnel as appropriate via email.

 GlaxoSmithKline	Document Name	207640 Protocol.doc		
	Type	Version	Document Identifier	Effective Date
	eldo_controlled	2.0; Most-Recent; Effective; CURRENT	090032d580d3df08	11-May-2017 13:45:31
	Reason For Issue	Auto Issue		

The initial report will be followed up with more information as relevant, or as requested by the GSKCH study manager.

7.5. Follow-up of Adverse Events and Serious Adverse Events

Follow-up of AEs and SAEs:

1. After the initial report, the investigator is required to proactively follow up with each subject and provide further information on the subject's condition.
2. All AEs/SAEs will be followed until resolution, until the condition stabilizes, until the event is otherwise explained, or until the subject is lost to follow-up.
3. The investigator is obligated to perform or arrange for the conduct of supplemental measurements and/or evaluations as may be indicated or as requested by GSK to elucidate as fully as possible the nature and/or causality of the AE or SAE.
4. Investigators are not obliged to actively seek AEs or SAEs in former subjects. However, if the investigator learns of any SAE, including the death, at any time after a subject has been discharged from the study, and considers the event reasonably related to the investigational product or study participation, the investigator will promptly notify GSKCH.
5. The investigator will submit any updated SAE data to GSK within the designated reporting time frames.

Regulatory and ethics reporting requirements for SAEs:

1. The investigator will promptly report all SAEs to GSKCH within the designated reporting timeframes (within 24 hours of learning of the event). GSKCH has a legal responsibility to notify, as appropriate, the local regulatory authority and other regulatory authorities about the safety of a product under clinical investigation. Prompt notification of SAEs by the investigator to GSKCH is essential so that legal obligations and ethical responsibilities towards the safety of subjects are met.
2. GSKCH will comply with country specific regulatory requirements relating to safety reporting to the regulatory authority, IEC and investigators.
3. Investigator safety reports are prepared according to GSKCH policy and are forwarded to investigators as necessary. An investigator safety report is prepared for a SAE(s) that is both attributable to investigational product and unexpected. The purpose of the report is to fulfill specific regulatory and GCP requirements, regarding the product under investigation.
4. An investigator who receives an investigator safety report describing a SAE(s) or other specific safety information (e.g., summary of listing of SAEs) from GSKCH will file it with the Investigator Brochure (or safety statement) and will notify the IEC, if appropriate according to local requirements.

 GlaxoSmithKline	Document Name	207640 Protocol.doc		
	Type	Version	Document Identifier	Effective Date
	eldo_controlled	2.0; Most-Recent; Effective; CURRENT	090032d580d3df08	11-May-2017 13:45:31
	Reason For Issue	Auto Issue		

